1.1 Background and Significance

Recurrent malignant pleural effusion (MPE) is a debilitating condition, which is associated with a significant morbidity and worsening of quality of life (QOL). Overall median survival of patients with MPE is poor and it changes slightly by histology: breast cancer, 7.4 months; non-small cell lung cancer, 4.3 months; and ovarian cancer, 9.4 months (1). Therapy of MPE is symptomatic and palliative, and consists of mechanical evacuation of the effusion to relieve pulmonary compression and dyspnea. There are no well-established methods of therapy, and the techniques used vary. They include repeated thoracentesis with small-bore catheters, tube thoracostomy, or video-assisted thoracic surgery for optimal drainage. Pleurodesis may be induced chemically by talc, tetracycline, doxycycline, bleomycin, or instillation of talc slurry(1). Patient selection is required since these techniques may be associated with complications (2). Several studies examined the utility of intrapleural drug administration for management of MPE. In a randomized trial, methylprednisolone did not delay reaccumulation of symptomatic pleural effusion compared to placebo (3). Immunotherapy with OK-432 had been shown to be feasible and active for MPE in a small-randomized trial (4). Recently a chronic indwelling pleural catheter has been introduced for the therapy of MPE. A randomized study examined its safety and efficacy versus tube thoracostomy and doxycycline sclerosis(5). Outpatient treatment with indwelling pleural catheter was found to be safe and equivalent in efficacy to treatment with tube thoracostomy(5). In addition, it was associated with fewer hospitalization days and was less expensive than inpatient methods(6). Our common practice in recent years had been placement of the indwelling pleural catheter in all patients who had reaccumulation of symptomatic malignant pleural effusion.

Tumor-Initiating Cells (TICs) in MPE

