In an IRB-approved laboratory study we cultured pleural effusion cells as spheres in tumor-initiating culture conditions (17, 18) and completed fresh flow cytometry analysis of the percentage of CD44+CD24-/lo epithelial cells (detected as CD45-CD326+ CD44+CD24-/lo cells) from 29 unselected patients with metastatic breast cancer who underwent pleurocentesis for symptomatic pleural effusion (Figure 1). In this exploratory analysis, we retrospectively examined the association between TICs and overall survival from the time of pleurocentesis and report that patients with higher percentages of TICs in the pleural fluid had significantly shorter overall survival than those with fewer TICs.

We analyzed fresh MPE samples from 29 pts with breast cancer for epithelial cells with a tumor-initiating cell phenotype (TIC, CD45-CD326+ CD44+CD24-/lo): CD45- (leukocyte

marker), CD326+ (also known as EpCAM an epithelial marker), and CD44+ and CD24-/lo (tumor-initiating markers), using multicolor flow cytometry on an IRB-approved protocol. Overall survival (OS) was measured from time of MPE assessment. Univariate analyses of survival were performed using Cox proportional hazards (CPH), with 1-year levels computed using the method of Kaplan-Meier. Multivariate analyses were performed using the CPH model. Median follow-up was 4.1 months, range 0.2 to 28.9. Eighteen patients have died of disease. Median percentage of CD45-CD326+ cells was 1.24% which contained a median TIC component of 9.5%. On univariate analysis, higher level of %TICs were significantly associated with differences in overall survival (Figure 2, $P = 0.005$). Actuarial 1-yr OS was 24% vs. 77% for patients with %TIC above (TIChi) and below (TIClo) the median ($P = 0.016$). Increasing percentage of TICs remained a significant predictor for worse OS on multivariate analysis (hazard ratio 1.25, confidence interval 1.06-1.49, $P = 0.007$). An increased percentage of TICs predicted for decreased OS among patients with MPE consistent with the hypothesis that these cells mediate recurrence and death from breast cancer.

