5.0 Treatment Plan

5.0 Treatment Plan

Chronic dosing has been suggested to be more effective for targeted therapies in pre-clincial studies. As such a dosing regimen found to be relatively non-toxic has been selected for chronic administration with concurrent standard agents (details above). Patients will initially receive daily oral VPA 15 mg/kg/day divided in three doses or placebo divided into three doses. Based on the patient's bmi, obese patient dosing will be based on the adjusted body weight calculated using the MD Anderson Clinical Calculator Formula (<http://inside2.mdanderson.org/apps/calculators/calc1.cfm>). Body mass index is a measure of body fat based on height and weight (applies to both men and women adults)

BMI	Weight Status
-----	---------------

Below 18.5	Underweight
18.5 – 24.9	Normal
25.0 – 29.9	Overweight
30.0 and Above	Obese

If the patient tolerates the reduced dose for 10 consecutive days then the VPA dose will increase to 30 mg/kg/day divided into three doses or placebo divided into three doses. The patient will be contacted by phone to assess tolerance and instruction to increase dose. Daily dose in mg will be divided by 250 mg and rounded down to a whole number of capsules to determine the number of VPA tablets or placebo tablets to be taken 3 times per day. Depending on the time of indwelling pleural catheter placement, on day 1 of treatment the patient may take 1, 2, or 3 doses. The research team will instruct the patient on the number of doses to take on day 1. Patients will be instructed to take the VPA at approximately the same time each day. Patients will be instructed to take the pills with food. Study drug compliance will be verified by a returned pill diary. Patients will be treated for 10 weeks. We anticipate this study will be activated in January 2014 and will be completed in January 2016.

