6.0 Statistical Considerations

6.0 Statistical Considerations

Sample Size

The primary outcome for this study is time to pleural catheter removal because it is no longer needed to drain the pleura of fluid. Patients who have their catheter removed for other reasons will be censored as of the date of catheter removal. Patients who die before having their catheter removed will be censored on the date of death.

Preliminary data from 58 breast cancer patients with ECOG performance status 0, 1, 2, or 3 revealed a median time to catheter removal of 110 days with 95% confidence interval 56 to 328 days. Twenty-nine of these 58 patients had their catheters removed because they were no longer needed to drain the pleura of fluid.

Patients will be randomized to active treatment (valproic acid) or control. A sample size of 76 patients (38 on each arm) will yield 80% power to detect an improvement in median time to catheter removal from 56 days in the control arm to 28 days (hazard ratio = 2.0) in the active treatment arm with a 2-sided significance level of 0.05. We expect to enroll 3 patients per month. We will be able to detect a hazard ratio of 2.0 (control vs. experimental), regardless of the median for the control group. If the median for the control group is actually 110 days, then we will be able to detect a significant difference if the median in the experimental group is 55 days.

This sample size calculation includes an interim analysis for futility and for efficacy once 36 patients have had their catheters removed using the methods of Lan and DeMets. The interim analysis for efficacy will employ an O'Brien-Fleming stopping boundary with a nominal significance level of 0.0031, while the interim analysis for futility will employ a Pockock stopping boundary with a nominal significance level of 0.3217. The final analysis will use a nominal significance level of 0.049 and will be conducted after all patients have had their catheters removed. These sample size calculations were performed with East 5.0 (Copyright © 2007, Cytel Inc., Cambridge, MA). Sample size was calculated based on 50% reduction in median time to catheter removal secondary to improved fluid in the control.

Randomization

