Operating Characteristics of Toxicity Monitoring Rule					
Rate of Toxicity Leading to Dose Reduction	Probability of Stopping Early	Sample Size			
		P_{25}	P_{50}	P_{75}	
0.20	0.020	40	40	40	
0.25	0.071	40	40	40	
0.30	0.205	40	40	40	
0.35	0.407	20	40	40	
0.40	0.636	15	30	40	
0.45	0.827	10	20	35	

Analysis

We will use summary statistics to describe the demographic and clinical characteristics of patients on each treatment arm.

Primary Outcome

Time to catheter removal will be measured from the date of placement of the catheter to the date it is removed. Removal of the catheter because it is no longer needed to drain the pleura will be considered an event. Removal of the catheter for other reasons will be considered competing risks. Patients who die before their catheter is removed will be considered censored on the date of death. We will use the methods described by Gooley et al. (1999) to estimate the cumulative distribution of time to catheter removal stratified by treatment arm and randomization strata.

We will use Cox (1972) proportional hazards regression to model time to catheter removal as a function of treatment arm, cytology, and lung re-expansion, as well as other potential prognostic factors, including ECOG performance status, the number of circulating tumor cells in the peripheral blood and in the pleural effusion.

Secondary Outcomes

We will use summary statistics to describe the amount of pleural fluid drainage by treatment arm, and we will use a two-sample t-test to compare treatment arms with respect to the mean amount of pleural fluid drainage. If the usual normality assumptions do not hold we will use the Mann-Whitney test to compare treatment arms with respect to the median amount of pleural fluid drainage.

We will compare treatment arms with respect to tumor burden using a Cochran-Mantel-Haenszel chi-square test stratified by concomitant therapy. Tumor burden will be assessed with chest cat scan during week 10.

We will use summary statistics to describe symptom burden dyspnea and exercise tolerance changes and dyspnea as measured by the EQ-5D and St George's respiratory questionnaire at baseline and again at weeks 2, 6, and 10. We will use repeated measures analysis of variance methods to assess differences between treatment arms with respect to QOL, dyspnea and exercise tolerance

Toxicity

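### Censoring death with the catheter in place makes the planned cumulative removal curve overstate successful removal in each arm

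*Combined protocol and SAP*

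**What the plan says.** In Section 6.0, Analysis, Primary Outcome, the event is removal of the catheter because drainage is no longer needed. Two rules for the other endings follow: "Removal of the catheter for other reasons will be considered competing risks" and "Patients who die before their catheter is removed will be considered censored on the date of death". The plan then uses a competing-risks method "to estimate the cumulative distribution of time to catheter removal stratified by treatment arm and randomization strata". A Cox model for time to removal follows.

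The Sample Size paragraph of the same section agrees on death ("Patients who die before having their catheter removed will be censored on the date of death") but words other-reason removal differently: "Patients who have their catheter removed for other reasons will be censored as of the date of catheter removal". Nothing elsewhere in the analysis plan makes death a competing event. Section 7.1, however, lists death with the catheter in place as a treatment failure, beside blockage, infection and other unplanned removals.

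**The concern.** A censored patient is assumed to have the same future chance of the event as those still under observation. That is reasonable for someone alive with a catheter at last contact. It cannot hold for someone who has died. With respect to death, the planned estimate is therefore one minus Kaplan-Meier: the probability belonging to the dead is handed to the survivors, and the curve no longer gives the share of patients actually freed of the catheter.

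The plan already accepts this logic for other-reason removals. It states no estimand of the kind that asks what would happen if nobody died, and such an estimand would sit oddly beside a competing-risks treatment of the other removals.

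At stake are the plan's absolute estimates for its primary outcome: the probability of successful removal by a given time, and the median read from the curve. The difference between arms read from the curves can also shift, in either direction.

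**Working it through.** **Plan's own figure.** The documents give no value for the cumulative curve, so there is none to reproduce. The planning medians do agree with the stated hazard ratio: 56/28 = 2.0 and 110/55 = 2.0.

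**Inputs from the documents**
- Removal medians of 110 and 55, and 56 and 28 days (Section 6.0, Sample Size), taken as cause-specific.
- Survival: "Overall median survival of patients with MPE is poor and it changes slightly by histology: breast cancer, 7.4 months" (Section 1.1), about 225 days.
- A second survival source in Section 1.1: "Actuarial 1-yr OS was 24% vs. 77% for patients with %TIC above (TIChi) and below (TIClo) the median". The average is (0.24 + 0.77)/2 = 0.505, which under an exponential gives a median of 365 × ln 2 / (−ln 0.505) ≈ 370 days. It rests on only 29 patients.
- 38 patients per arm (Section 6.0).
- Reading times. Section 6.0 sets none. Day 70 is the end of treatment ("Patients will be treated for 10 weeks", Section 5.0). Day 180 is the point after which Section 7.1 counts a catheter still in place as a failure.

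**Assumptions.** Constant, independent hazards; the same death hazard in both arms; survival counted from catheter placement; no other-reason removals at first. Death medians of 225, 365 and 730 days show the range.

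**Formulas.** Let λ = ln 2 / removal median and δ = ln 2 / death median.
- Planned curve (death censored): 1 − exp(−λt)
- Cumulative incidence (death competing): λ/(λ+δ) × [1 − exp(−(λ+δ)t)]
- Deaths with catheter in place per 38: 38 × δ/(λ+δ) × [1 − exp(−(λ+δ)t)]

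**One case in full.** Removal median 110, death median 225, t = 180: λ = 0.006301, δ = 0.003081. The planned curve gives 1 − exp(−1.134) = 67.8%. The cumulative incidence is 0.6716 × (1 − 0.1847) = 54.8%. The overstatement, from unrounded values, is 13.1 points.

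**Planned against true, death median 225 days**

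| Removal median | Day 70 | Excess | Day 180 | Excess | Deaths in place per 38 by day 70 / 180 |
|---|---|---|---|---|---|
| 110 d | 35.7 vs 32.3% | 3.3 | 67.8 vs 54.8% | 13.1 | 6.0 / 10.2 |
| 55 d | 58.6 vs 53.6% | 5.1 | 89.7 vs 75.6% | 14.1 | 5.0 / 7.0 |
| 56 d | 58.0 vs 52.9% | 5.0 | 89.2 vs 75.1% | 14.1 | 5.0 / 7.1 |
| 28 d | 82.3 vs 76.3% | 6.1 | 98.8 vs 88.3% | 10.5 | 3.6 / 4.2 |

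**Sensitivity of the excess, in points (removal medians 110, 55, 56, 28)**

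| Scenario | Day 70 | Day 180 |
|---|---|---|
| Death median 365 d | 2.1, 3.2, 3.2, 3.8 | 8.6, 9.1, 9.2, 6.7 |
| Death median 730 d | 1.1, 1.6, 1.6, 1.9 | 4.5, 4.8, 4.8, 3.5 |
| Death 225 d, other-reason removals also competing (assumed median 365 d) | 3.1, 4.7, 4.6, 5.6 | 10.8, 11.9, 11.9, 9.3 |

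**Time to 50% removed.** The planned curve returns the input medians 110, 55, 56 and 28 days. With death competing, the times are 145, 62, 63 and 30 days (225-day deaths) or 128, 59, 60 and 29 days (365-day deaths).

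**Difference between arms, planned against true (225-day deaths).** For 110/55: 22.9 vs 21.2 points at day 70 and 21.8 vs 20.8 at day 180. For 56/28: 24.4 vs 23.3 and 9.6 vs 13.2.

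**Simulation check.** In 4,000 simulated arms of 38 per scenario (225-day deaths), the mean estimates agree with the formulas to within 0.2 points. The standard error of the competing-risks estimate is 7.1 to 8.2 points at day 70 and 5.4 to 8.1 at day 180. The bias is therefore below one standard error at day 70 (largest 6.1/7.1 = 0.9) and 1.6 to 2.0 standard errors at day 180 (13.1/8.1 to 14.1/7.0). In a second simulation, which added other-reason removals with a 365-day median, the planned estimate at day 180 was never lower and was strictly higher in 97.9% to 99.9% of arms.

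**The case against.** The direction of the bias is hard to dispute; its weight can be.

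- **Primary comparison.** The Cox model compares cause-specific hazards, where censoring deaths is usual. Its hazard ratio and test do not change. This stands in full.
- **Difference between arms.** The shifts above are 1.0 to 3.6 points. Combining the arm-level standard errors gives about 9 to 11 points for a difference (for example √(7.1² + 5.4²) = 8.9), so no shift exceeds about 0.4 standard errors. This also stands: the damage is to the absolute estimates, far more than to the contrast.
- **Stratum-level curves.** Read literally, the plan draws curves by arm and stratum. Two arms × two re-expansion levels × three performance-status levels make 12 cells, about 76/12 ≈ 6 patients each. With 6 per cell the standard error is about 17 to 21 points at day 70 and 14 to 21 at day 180, and the bias falls to 0.2 to 0.3 and 0.6 to 0.7 standard errors. The standard-error comparison in the check therefore holds only for curves pooled within arm. The bias in points is the same for the same hazards.
- **Source of the death rate.** The 7.4 months describes breast cancer patients with malignant effusion in general. It is neither this eligible population nor measured from catheter placement. That is why a range is shown. If survival is longer, the bias is smaller but keeps its sign.
- **Wording conflict.** Calling other-reason removals censored in one place and competing in another gives the same Cox analysis; it matters only for the curve.

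None of this makes the planned curve an estimate of the probability of successful removal.

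**Conclusion.** The concern holds. As written, the cumulative curve overstates successful removal in any arm where a death with the catheter in place precedes a later successful removal, and it can never understate it relative to the estimate that counts death as competing. That result is algebraic and needs no assumption about rates.

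The size does need assumptions. Across death medians of 225 to 730 days it is about 1 to 6 points at day 70 and 3.5 to 14 points at day 180, under constant independent hazards with equal mortality by arm and no other-reason removals. The upper end uses the protocol's own survival figure. It should be corrected before analysis, but it does not threaten the primary test, the sample size or the follow-up.

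**What to change.** **Section 6.0, Primary Outcome.** State that, in the cumulative-incidence estimate, both removal for other reasons and death with the catheter in place are competing events, and that only patients alive with the catheter in place at last follow-up are censored. Label the Cox model as cause-specific: both kinds of ending stop a patient's time at risk, exactly as now.

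**Section 6.0, Sample Size.** Use the same wording, so that the two paragraphs no longer differ on other-reason removals.

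While editing, it would help to fix the reading times for the curves, to say whether they are pooled within arm or drawn by stratum, and to say how a catheter still in place after 180 days (Section 7.1) enters the estimate.

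**Cost.** Wording only. Section 3.4 already has the record followed for the date of removal or death, whichever is first. Reported removal percentages will be lower and medians longer, and those medians will not be directly comparable with the planning medians if the latter came from curves that censored deaths. The report should say so.

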2.0 Objectives

2.0 Study Objectives

2.1 Research Design and Methods

Our goal is to better understand the biology of breast cancer stem cells and pleural effusion formation to improve therapy of malignant pleural effusion in breast cancer patients. Based on our preclinical studies described in the background section, a clinical trial is planned to answer specific questions regarding the role of histone deacetylation and effect of its inhibition on breast patients with MPE. In this study, eligible patients with recurrent symptomatic MPE who need an indwelling pleural catheter based on MDACC algorithms for placement will have one placed and will receive 10 weeks of VPA or placebo.

The first aim is to achieve a beneficial clinical effect of VPA on patients with MPE. The specific question is if VPA alters pleural effusion re-accumulation following placement of an indwelling pleural catheter to the extent that it will enable significant shortening of time to removal of the catheter compared to placebo. Additional aims will analyze the biology of histone deacetylation inhibition in MPE and will help to develop biomarkers of activity and noninvasive monitoring to such therapy:

The second aim is to analyze the amount of daily fluid drained with therapy. Patients will be provided a daily fluid drainage diary.

The third aim is to assess radiographic and clinical correlates using standard of care testing and assessment: Chest x-ray and CT to study effect on primary tumor burden and assessment of overall survival.

Our fourth aim is to study biological correlates. We will study the level of H3 and h4 hyperacetylation and inflammatory cytokines in the effusion and in the serum at baseline and at week 2. Fluid will be collected and stored if applicable from visits at baseline, at week 2, 6, and 10. We plan to study expression of stem cell markers on cells from effusion to demonstrate inhibitory effect of VPA on these cells. Urine will be collected and stored if applicable at baseline, weeks 2, 6, and 10 for correlative studies. Finally, we will study the effect of VPA therapy on level of circulating tumor cells.

Our fifth aim is to assess drug effect on patient symptoms, dyspnea and exercise tolerance using the EuroQOL, St George's respiratory questionnare and six-minute walk test respectively.

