3.4 On-Study Evaluations

On the day of indwelling intrapleural catheter placement the patient's pleural fluid will be drained, recorded and sent for cytology review. On the day of indwelling intrapleural catheter placement patients will receive VPA or **placebo** if cytology is positive. Patients will be provided a diary to record drainage from home.

Patients will be treated for the whole period of 10 weeks, and clinical course of disease will be monitored throughout this time. (Note: evaluations may be done within \pm 7 business days of the date specified in the protocol).

Patients will initially receive daily oral VPA 15 mg/kg/day divided in three doses or placebo divided in three doses. Based on the patient's bmi, obese patient dosing will be based on the adjusted body weight calculated using the MD Anderson Clinical

Calculator Formula (<http://inside2.mdanderson.org/apps/calculators/calc1.cfm>). If the patient tolerates the reduced dose for 10 consecutive days then the VPA dose will increase to 30 mg/kg/day divided into three doses or placebo divided into three doses. The patient will be contacted by phone to assess tolerance and instruction to increase dose. Daily dose in mg will be divided by 250 mg and rounded down to a whole number of capsules to determine the number of VPA tablets or placebo tablets to be taken 3 times per day.

Evaluations may occur any time during weeks 2, 6, and 10.

- 3.4.1 Patients will document daily amount of pleural fluid drainage.
- 3.4.2 Patients will be evaluated at weeks 2, 6, and 10 with complete interim histories and physical examinations including measurement of vital signs, performance status, weight and medical history.
- 3.4.3 Patients will complete a EQ-5D and St. George's respiratory questionnaire, at weeks 2, 6, and 10 in person, via telephone or electronic media.
- 3.4.4 Blood samples for CBC with differential, platelet count, and PT/PTT/INR, serum and plasma banking, and optional CTC (if patient agrees) assessment will be collected prior to treatment and at weeks 2, 6 and 10.
- 3.4.5 Tests to measure serum electrolytes, BUN, creatinine, glucose, albumin, alkaline phosphatase, AST or ALT, LDH, total bilirubin, amylase, lipase, magnesium and ionized calcium will be performed at weeks 2, 6, and 10.
- 3.4.6 Optional urine (if patient agrees) will be collected prior to treatment and at weeks 2, 6 and 10.
- 3.4.7 Chest x-ray will be performed immediately after catheter placement and at weeks 2, 6, and 10.

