Patients will be randomized to active treatment or control stratified by lung re-expansion ($\geq 80\%$ lung re-expansion, $<80\%$ lung re-expansion), ECOG performance status (0-1, 2, 3), using the Clinical Trial Conduct website (<https://biostatsitics.mdanderson.org/ClinicalTrialConduct>), which is housed on a secure server at MDACC and maintained by the MDACC Department of Biostatistics. Access to the website will be gained through usernames and passwords provided by the MDACC Department of Biostatistics to personnel responsible for enrolling patients and reviewing and analyzing patient data. Training on the use of the Clinical Trial Conduct website to randomize and enroll patients on the study will be provided by the study statistician. Investigation Pharmacy will have access the Clinical Trial Conduct website

to review the patient assignment. The IND office will be notified if an event occurs leading to the un-blinding of the randomization.

Toxicity Monitoring

We will use the methods described by Thall et al. (1995) to monitor the rate of toxicity leading to dose reduction for patients on active treatment. Because the study is blinded to the investigators, the study statistician will monitor the toxicity monitoring rule for the active treatment arm. Toxicity data leading to dose reduction will be forwarded to the study statistician as they accrue in the form of an email with the patient study identifier and a description of the toxicity leading to dose reduction.

If the rate of toxicity leading to dose reduction for patients on active treatment is more than 25% the study will be stopped. We will enroll a minimum of 10 and a maximum of 40 patients on active treatment. We will stop the study early if $P(\text{toxicity leading to dose reduction for patient on active treatment} > 25\% | \text{data from the study}) > 0.975$. That is, given the toxicity outcomes from the patients on active treatment, if we determine that there is more than a 97.5% chance that the rate of toxicity leading to dose reduction is more than 25% we will stop the study. This decision rule gives the following stopping rule. We assume a uniform prior distribution for the rate of toxicity leading to dose-reduction. Stop the study if

[# of pts on active treatment with toxicity leading to dose reduction / # of pts evaluated]
> 6/10, 8/15, 9/20, 11/25, 13/30, 14/35, 16/40

The operating characteristics of this study design are shown in the table below.

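### The drainage comparison uses neither the randomisation strata nor the placement volume, so it loses power if these predict drainage

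*Combined protocol and SAP*

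**What the plan says.** Drainage is the trial's second aim (section 2.1: "The second aim is to analyze the amount of daily fluid drained with therapy") and secondary objective 2.3.1. Section 6.0, Secondary Outcomes, sets out the comparison: "we will use a two-sample t-test to compare treatment arms with respect to the mean amount of pleural fluid drainage". If normality fails, "we will use the Mann-Whitney test to compare treatment arms with respect to the median amount of pleural fluid drainage". No section adds an adjusted or stratified analysis of drainage.

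Three other places bear on this:

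- **Randomisation (section 6.0).** "Patients will be randomized to active treatment or control stratified by lung re-expansion", with two levels, and by ECOG performance status with three levels (0-1, 2, 3), giving six cells. The allocation method within cells, including any block size, is not stated.
- **Primary outcome (section 6.0).** The cumulative distribution of time to removal is estimated by arm and randomisation strata. The Cox model contains lung re-expansion "as well as other potential prognostic factors, including ECOG performance status".
- **Placement day (section 3.4).** "On the day of indwelling intrapleural catheter placement the patient's pleural fluid will be drained, recorded and sent for cytology review". The schedule table in the same section also marks daily drainage documentation on that day.

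**The concern.** The plan treats lung re-expansion and ECOG status as important enough to stratify on and to model for catheter removal. Under section 7.1, removal is triggered by low drained volumes, so factors thought to predict removal plausibly predict drainage too. The drainage test nevertheless leaves them out, along with a baseline volume that is already recorded.

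Two effects follow if these variables are prognostic. First, variation that could be explained stays in the error term, which costs power. Second, if allocation is balanced within strata, the between-arm difference varies less than the t-test assumes. Its standard error is then too large, its confidence interval too wide, and its type I error less than the nominal 5%.

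Drainage is the direct measure of the trial's rationale, that valproate may reduce effusion production. With 38 patients per arm, precision is limited and a real effect on volume could be missed.

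**Working it through.** **Inputs from the plan.** 76 patients, 38 per arm; strata 2 x 3 = 6 cells (section 6.0). The two-sided 0.05 level is stated for the primary outcome and assumed here for drainage. The plan has no drainage power figure to reproduce: its 80% power is for a hazard ratio of 2.0 on time to catheter removal.

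**Assumed inputs.** The multiple correlation R between drainage and the covariates (strata plus placement volume), the share of drainage variance explained by the strata alone, the stratum prevalences, and permuted blocks of 4. None is in the documents.

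**1. Power.** For a standardised difference d, the noncentrality is d x sqrt(38/2) = d x 4.359. The t-test has 76 - 2 = 74 degrees of freedom and critical value 1.993. Power is 80% at d = 0.651 (noncentrality 2.839). The linear model adds one term for lung re-expansion, two for ECOG and one for placement volume, leaving 76 - 2 - 4 = 70 degrees of freedom (critical value 1.994). The residual SD shrinks by sqrt(1 - R²), so d becomes 0.651/sqrt(1 - R²).

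| R | R² | SE ratio sqrt(1 - R²) | d after adjustment | Power |
|---|---|---|---|---|
| 0 | 0 | 1.000 | 0.651 | 79.9% |
| 0.3 | 0.09 | 0.954 | 0.683 | 83.5% |
| 0.4 | 0.16 | 0.917 | 0.711 | 86.3% |
| 0.5 | 0.25 | 0.866 | 0.752 | 89.8% |
| 0.7 | 0.49 | 0.714 | 0.912 | 97.5% |

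Starting from 60% power (d = 0.514), R = 0.5 gives 72%.

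This formula ignores the small cost of chance imbalance in the covariates. Simulation of 6,000 trials per setting, with stratified blocks of 4, includes it:

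| Variance explained by strata / placement volume | t-test power | Adjusted power | SE ratio |
|---|---|---|---|
| 0 / 0 | 79.8% | 79.0% | 1.009 |
| 10% / 10% | 79.8% | 87.1% | 0.902 |
| 20% / 20% | 82.9% | 95.3% | 0.781 |

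**2. Type I error of the t-test.** Suppose the arms are perfectly balanced within strata and the strata explain a share R²s of the variance. The true variance of the difference is then (1 - R²s) times what the t-test estimates. The approximate true error rate is P(|t74| > 1.993/sqrt(1 - R²s)):

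- R²s = 0.10: threshold 2.10, about 3.9%
- R²s = 0.25: threshold 2.30, about 2.4%
- R²s = 0.40: threshold 2.57, about 1.2%

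Simulated null trials with blocks of 4 and one set of stratum prevalences gave 3.7% to 4.3%, 2.4% to 2.5%, and 1.3% to 1.5%. A second set of prevalences and stratum effects gave 3.9% at 0.10 and 3.0% to 3.4% at 0.20 to 0.25; the linear model stayed at 4.7% to 5.3% there. Under simple randomisation the t-test's error was about 5% (4.6% to 5.5%), even at R²s = 0.40. The conservatism therefore needs both prognostic strata and balanced allocation.

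**The case against.** The strongest reply is that nothing invalid is planned. In a randomised trial the unadjusted t-test estimates the arm difference without bias, and its type I error is at or below 5%. Drainage is a secondary outcome with no stated effect size or power, and the primary analysis already uses the strata. All of this stands, and it limits the point to efficiency.

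A reader might infer that the reported interval is certainly too wide and that power is certainly lost. The documents do not support that. They give no SD or correlation for drainage, and they call ECOG status a potential prognostic factor for catheter removal, not for volume. They also name no balancing method. If nothing is prognostic, adjustment gains nothing.

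A reader might also treat placement volume as a baseline value of the outcome itself. It is a single evacuation of accumulated fluid, whereas the outcome is daily drainage on therapy, and no section links the two. The schedule also marks drainage documentation on the placement day, so that volume could fall inside the outcome; it cannot be both outcome and covariate.

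Finally, the larger gap may be that the drainage summary and its window are undefined, and that drainage ends at removal or death. That is correct, and adjustment does not repair it. But whichever summary is chosen, the planned test would still be unadjusted.

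**Conclusion.** The point holds as a worthwhile, nearly free improvement to a secondary analysis. The planned test is valid but leaves out information the trial collects. The gain from 80% power is nil at R = 0, about 4 points at 0.3, 10 at 0.5 and 17 at 0.7. If nothing is prognostic, the cost is at most about one point (79.8% to 79.0% in simulation). These figures assume 38 evaluable patients per arm, a two-sided 0.05 level and a roughly normal summary. The type I error results further assume balanced allocation within strata. The trial's primary conclusion is unaffected.

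**What to change.** In section 6.0, Secondary Outcomes:

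1. Make the main comparison a linear model of the per-patient drainage summary. Terms: treatment arm, lung re-expansion stratum and ECOG stratum as randomised (merging ECOG 2 and 3 if a cell is very small), and placement volume as a baseline covariate. Report the adjusted difference with its 95% CI.
2. State that fluid drained on the placement day is excluded from the outcome.
3. If the data are skewed, either use a log scale with a stated rule for zero volumes and report a ratio of geometric means, or use a van Elteren test stratified by the randomisation strata with the same merging rule. The van Elteren test does not use placement volume, so it forgoes that part of any gain.
4. Keep the two-sample t-test as a supportive analysis.
5. State the allocation method within strata.

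The cost is SAP wording, one model and about 4 of 74 degrees of freedom. No new data are needed. The drainage window and the handling of removal and death must be defined separately.
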